#### **Waist Circumference:**

- 1. The participant should be standing erect but relaxed, with feet/ankles touching.
- 2. All measurements should be made after the participant has fully exhaled.
- 3. Viewing the participant from the front or rear, identify the smallest width of the waist;
- 4. measure circumference at that point. In each case, the measuring tape should be parallel to the floor during the measurement. Record the result in cm to the nearest millimeter/0.1 cm.
- 5. Repeat this procedure twice, with the participant fully exhaling between each measurement, so that in all 3 measurements are performed.
- 6. Follow instructions as per general information (Number 6), above.

Approved by: [name] No.: SARO.20.001
[name]	Version No.: 4.0

CONFIDENTIAL Page 108 of 109

#### 15.10 APPENDIX 10: PROTOCOL AMENDMENT TEMPLATE

Amendment Details		

**History of Amendments** 

A total of two XX global amendments have occurred, as shown in the table below:

Document	Sponsor Approval Date (dd/mmm/yyyy)	Approximate No Enrolled*

\*Subjects enrolled until the date of Sponsor approval date

**Current Amendment** 

The table below provides an overview of the current amendment.

Amendment Number:	
Approximate No Enrolled	
Summary of the Amendment:	

Summary of Changes in the Current Amendment:

Section # and Name	Description of Change	Brief Rationale for Change

The purpose of this document is to provide a description of the methods and procedures to be implemented for the presentation of safety data from Saroglitazar Magnesium 4 mg tablet, for trial SARO.20.001 version 4.0. This document is based on protocol dated 17th Nov 2023. Any revisions to this plan will be made prior to final analysis and reasons for such revisions will be described in the final Clinical Study Report. This study is terminated by sponsor's discretion and no primary efficacy endpoint data has been collected for any subject, hence no formal statistical analysis will be done for any efficacy endpoints. Hence, this safety data plan includes only data of screened and four subjects who were randomized in the study.

1 Objectives:**Safety Objectives:**

1. To evaluate the safety and tolerability of Saroglitazar Magnesium 4 mg.

2 Study Design:

This phase 2a study is a randomized, placebo-controlled, double-blind, multicenter parallel-arm trial to evaluate the safety and efficacy of Saroglitazar Magnesium 4 mg compared with placebo in NAFLD in PLWH.

Number of Subjects:

In total, approximately 120 participants (60 participants in each treatment arm) were planned to receive either Saroglitazar 4 mg or placebo.

Randomization

Participants were randomized in a 1:1 ratio to receive Saroglitazar Magnesium 4 mg once daily orally or Placebo. The randomization scheme will be stratified by clinical center. Treatment assignments are double masked throughout the study until all data collection for the trial has been completed (i.e., after completion of the post-trial follow-up for all participants). The block randomization schedule was generated using SAS[®] software (Version: 9.4 or higher; SAS Institute Inc., USA).

Blinding and Un-blinding

The study is a double blind study with randomized subjects being treated with Saroglitazar Magnesium 4 mg, or Placebo. The essential aim of blinding is to prevent identification of the treatments by the investigator, subject, and others associated with the conduct of the study until all such opportunities for bias have passed.

All members of the clinical study team, investigators and site staff will be blinded to treatment assignments while the study is in progress. In addition, Biostatistics staff who are directly involved in the analysis of the study results will remain blinded to treatment assignment while the study is in progress.

If necessary, the Sponsor may be required to unblind a subject if an adverse event (AE) meets criteria of a Suspected Unexpected Serious Adverse Reaction (SUSAR) in order to fulfil expedited regulatory reporting requirements. In this event, the Sponsor Medical Expert will not divulge the treatment code to

any other personnel involved in reporting, obtaining, and/or reviewing the clinical evaluations. This level of blinding will be maintained throughout the conduct of the study.

In the event of a medical emergency during the study where the knowledge of subject treatment is required, an individual Principal Investigator will have the ability to unmask the treatment assignment for a specific subject. The Investigator should notify the Sponsor prior to unmasking a subject if there is sufficient time. Further, the Sponsor must be informed whenever the randomization code is broken. The reason for unblinding should be clearly and fully documented by the Investigator.

Once all study data have been verified, validated, and the database is locked, individual subjects will be unmasked to their treatment.

During this study, no unblinding done due to any safety reason.

[figure not shown]
[figure not shown]
SAFETY DATA PLAN

FOR

SARO.20.001

CONFIDENTIAL

PAGE 7 OF 12

[figure not shown]
SAFETY DATA PLAN

FOR

SARO.20.001

CONFIDENTIAL

PAGE 8 OF 12

4 Protocol Deviations/ Violations/ Changes from Protocol:

Protocol deviation will be included in CSR.

For the purposes of this study, no distinction will be made between protocol violation and deviation. Deviation may be categorized as minor protocol deviation or major protocol deviation. Classification of protocol deviations as major or minor will be assessed at the blinded data review meeting prior to database lock. Minor protocol deviation includes any deviation that do not necessarily influence the results/outcome of primary endpoints or participant safety. Minor protocol deviation does not require immediate notification to the IRB unless otherwise specified by IRB requirements. All minor protocol deviations will be noted in monitoring reports and discuss with investigator/site personal. Major protocol deviation includes any violation, which may influence the results/outcome of primary endpoints or participant safety. Major protocol deviation must be reported immediately to the IRB, as specified by the IRB requirements. All major protocol deviations will be reported to the sponsor immediately (Note: persistent non-compliance of minor protocol deviations may rise to the level of major protocol deviations). As a result of protocol deviations, corrective actions are to be developed and implemented promptly.

The sponsor reserves the right to terminate the study at a given center in the event of monitoring and/or auditing findings of serious or persistent non-compliance with the protocol, Standard Operating Procedures (SOPs), GCP, and/or applicable regulatory requirement(s) by an investigator/Institution. In all cases of site closure due to protocol deviations, the IRB and regulatory authority will be informed. The clinical study report (CSR) will provide a list of protocol deviations/violations in a separate section. The results will be analyzed for all participants regardless of protocol deviation occurrence.

Protocol deviations/violations will include but are not limited to the following:

- Violations of inclusion and exclusion criteria at randomization.
- Participants who met the withdrawal criteria but were not withdrawn.
- Participants who received the wrong treatment or incorrect dose.
- Participants who received an excluded medication.
- Serious non-compliance with regulatory or GCP guidelines.

5 Concomitant Therapy:

All medications recorded during the study will be coded using the World Health Organization (WHO) Drug Dictionary (latest version). A summary will be provided for the frequency and percent of participants who had concomitant therapy/medications. Summaries will be provided by Anatomical Therapeutic Chemical (ATC) classification level 3 term and Preferred Name.

Refer the protocol section 8.8 Concomitant Medications in detailed for the previous and concomitant medications, Permitted, prohibited Concomitant Medications and other restrictions.

6 Analysis Populations:

All Enrolled Population: includes all participants who signed an ICF. This analysis population will be used to summarize participant disposition.

Safety Population: includes all participants who received at least one dose of study drug. Participants in the safety analysis population will be analysed according to the treatment received. This analysis population will be used for all safety analyses.

7 Demographic and Baseline Characteristics:

Demographic and baseline characteristics include age in years, gender, ethnicity, race, height (cm), weight (kg), body mass index (kg/m²), hip (cm) and waist circumference (cm).

Demographic and baseline characteristics will be summarized for safety populations.

All the continuous variables (i.e., age, height etc.) will be summarized by n, mean, standard deviation, minimum, median and maximum values. All the categorical variables (i.e., gender) will be summarized as frequency and percentage.

8 Disposition of Subjects:

The number of subjects treated will be summarized.

The following summaries (number and/or percentage) will be included in the disposition table:

All enrolled subjects

Subjects in safety population

Subjects who completed the study

Subjects who discontinued from the study with reason for discontinuation

9 Medical History

The frequency count and percentage of patients experiencing any medical conditions will be tabulated by system organ classifications (SOC) and preferred term (PT) of MedDRA for all patients. The denominators for calculating the percentages will be based on number of patients in Safety Population. A data listing of medical history including medical and surgical history will be provided for Safety Population.

10 Data handling methodology:

Listing of subject data and tabulation of descriptive statistics be performed primarily using SAS[®] (version 9.4 or higher; SAS Institute Inc., USA).

The continuous variables will be summarized by n, mean, standard deviation, minimum, median and maximum. Categorical variables will be summarized with frequency and percentage.

10.1 Derived and Transformed Data:

Baseline:

In general, baseline will be defined as the last available, non-missing assessment prior to the administration of study assigned treatment.

10.2 Decimal Precision:

Unless otherwise noted, mean, median, standard deviation, minimum, maximum, percentage and any corresponding confidence interval will be presented to two decimal places.

10.3 Coding Dictionaries:

Adverse Events will be coded using the latest Medical Dictionary for Regulatory Activities (MedDRA).

The actual dictionary versions used will be presented in the Clinical Study Report.

10.4 Values of Clinical Significance:

Reference ranges for all laboratory parameters collected throughout the study are provided by the respective laboratory. A laboratory value that is outside of the reference range is considered either high abnormal (value above the upper limit of the reference range) or low abnormal (value below the lower limit of the reference range).

Note: a high abnormal or low abnormal laboratory value is not necessarily of clinical significance.

The laboratory reference ranges will be provided on the listings of standardized laboratory data with out of range values flagged (low or high).

11 Handling of Drop-outs/ Premature Withdrawal:

All data compiled up to the point of discontinuation will be used for the data presentation. All withdrawals will be included in all analyses up to the time of withdrawal. Subjects who are withdrawn prematurely from study treatment will be included in all analyses regardless of the duration of treatment.

12 Statistical Methods and Analysis:

The data collected from CRF and laboratory test reports will be analyzed for demographics and safety. All data in the database will be presented in the data listings. Unless otherwise stated, all listings will be presented by treatments and sorted by subject number and assessment date/time.

Demographic and baseline characteristics will be summarized by treatment. Subject disposition and reason for withdrawal will be listed and summarized. Unless otherwise stated, all the continuous variables will be represented by n, mean, standard deviation, minimum, median and maximum. All the categorical variables will be presented as frequency and percentage.

The change from baseline will be determined as:

Change = (last observed post dose value – pre dose).

13 Safety Analysis:

Subjects in safety population will be considered for the safety analysis.

13.1 Adverse Events:

Adverse Events will be coded using the MedDRA dictionary. Adverse Events will be grouped by SOC and PT and summarized by study treatment.

The summary tables will include the number of subjects and the number of events. For summaries by SOC and PT, a subject will be counted once at the SOC level and once at each PT within the SOC level.

- Relationships of definitely related, probably related, potentially related and Unknown will be judged as being treatment-related for the summary tables. Assessment of safety will be based on the frequency of TEAEs. All TEAEs seen during the study period will be listed. Separate listing will be provided for TEAE leading to discontinuation/other clinically significant non-fatal AE. Incidence of all TEAEs reported during the study in either of the group will be summarized by causality, severity and seriousness. Summaries for SAEs if any will also be provided.

The following AE tables will be provided:

- Overall Summary of Adverse Events by treatment
- Summary of Treatment Emergent Adverse Events by system organ class and preferred term
- Summary of Treatment Emergent Adverse Events by system organ class and preferred term by Severity.

13.2 Laboratory Evaluations:

Listings of individual subject laboratory results will be provided. Laboratory results and change from pre-dose values for lab tests will be summarized, at scheduled visits.

For summary purposes, laboratory values that are listed as above or below particular thresholds will be numerically listed as above or below that threshold, respectively, by the minimum measured amount for that parameter. For example, if a parameter is measured to two decimal places, and has a result of “> 6” then, for summary purposes, the value of 6.01 will be used. Values with “<” or “>” will be classified as Low or High, respectively, unless such classifications aren’t applicable for that parameter, in which case they will be classified as Normal.

13.3 Physical examinations:

All the physical examination will be listed by Subject no. by treatment.

13.4 Vital Signs:

Vital signs (systolic/diastolic blood pressure, heart rate, respiratory rate and body temperature) will be listed at each protocol scheduled visit.

All the vital signs will be listed by Subject no. by treatment.

14 Revision History:

Version No.	Revision History	Reason for change
Not Applicable	Not Applicable	Not Applicable

15 Reference:

Protocol: SARO.20.001 (Version 4.0).

16 Appendix:

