#### 11. STATISTICAL CONSIDERATIONS

#### 11.1 GENERAL CONSIDERATIONS

A separate Statistical Analysis Plan (SAP) will be prepared and finalized before database lock. SAP will provide further details regarding the definition of analysis variables and analysis methodology to address all study objectives. The SAP will serve as a compliment to the protocol and supersedes it in case of differences.

The statistical evaluation will be performed using SAS® software version 9.4 or higher (SAS Institute, Cary, NC). All data will be listed and summary tables will be provided. Summary statistics will be presented by treatment group. Continuous variables will be summarized for the measured values and change from baseline values using the number of observations, mean, standard deviation, median, minimum, and maximum. Categorical variables will be summarized with counts and percent for each category.

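### Does the SAP need to tie its Low/High labels for '<' and '>' laboratory results to the reference range?

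*SAP*

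**What the plan says.** Two places in the SAP deal with low and high laboratory values.

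- **SAP 10.4 (Values of Clinical Significance)** works from the laboratory's reference range: "A laboratory value that is outside of the reference range is considered either high abnormal" when it lies above the upper limit, or low abnormal when it lies below the lower limit. The same section sends this to the listings, which show the reference ranges "with out of range values flagged (low or high").
- **SAP 13.2 (Laboratory Evaluations)** deals with results that the laboratory reports only as an inequality. Its paragraph opens: "For summary purposes, laboratory values that are listed as above or below particular thresholds" are to be replaced by a number one measurement unit beyond the threshold. For a result of '> 6' measured to two decimals, "for summary purposes, the value of 6.01 will be used". The closing sentence says that results with '<' or '>' "will be classified as Low or High, respectively, unless such classifications" are not "applicable for that parameter, in which case they will be classified as Normal".

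The outputs that 13.2 names are individual listings and summaries of results and of change from the pre-dose value at scheduled visits. SAP section 12 adds that "All data in the database will be presented in the data listings". Protocol 11.9.4 plans low/normal/high categories by normal range with shift tables, but Protocol 11.1 settles which document governs: "The SAP will serve as a compliment to the protocol and supersedes it in case of differences".

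**The concern.** The closing sentence of 13.2 assigns Low or High from the inequality sign, with an exception that works by parameter and has no stated criterion. It does not ask where the reporting limit sits relative to the reference range. A result of '> 6' tells us only that the value exceeds 6. If the upper limit of normal were 8, the value could be 6.5 (normal) or 9 (high), and calling it High would claim more than the laboratory reported. The exception does not clearly help, since a parameter with a real upper limit would ordinarily be one for which High is applicable.

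The same result could then be labelled High under 13.2 and left unflagged in a listing under 10.4, with nothing in the text to say which prevails. In a trial with laboratory shift tables and many subjects, such a rule could inflate the count of treatment-emergent abnormalities. Laboratory safety is part of what this SAP reports, so the point deserves a check.

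**Working it through.** **Inputs from the SAP.** The substitution rule, the symbol rule and its exception (13.2); the reference-range rule (10.4). The documents give no reference ranges and no reporting limits, so every range below is an assumption made only to see when the rules part.

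**Step 1. Reproduce the plan's figure.** For a threshold *c* measured to *k* decimals, the step is *d* = 10^(−*k*). '> *c*' becomes *c* + *d* and '< *c*' becomes *c* − *d*. With *c* = 6 and *k* = 2, 6 + 0.01 = 6.01, as the SAP states. The mirror case is 6 − 0.01 = 5.99.

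**Step 2. Apply both rules to the same result.** The 10.4 column compares the substituted value with the assumed range. The SAP does not itself prescribe that comparison.

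| Result | Assumed range | Substitute | 13.2 label | 10.4 on the substitute | Classes the true value could have |
|---|---|---|---|---|---|
| > 6 | 4 to 8 | 6.01 | High | Normal | Normal or High |
| > 6 | 4 to 6 | 6.01 | High | High | High |
| > 6 | 2 to 5 | 6.01 | High | High | High |
| > 6 | 4, no upper limit | 6.01 | Normal (exception) | Normal | Normal |
| < 6 | 4 to 8 | 5.99 | Low | Normal | Low or Normal |
| < 6 | 6 to 8 | 5.99 | Low | Low | Low |
| < 6 | 7 to 9 | 5.99 | Low | Low | Low |
| < 6 | no lower limit, 8 | 5.99 | Normal (exception) | Normal | Normal |

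**Step 3. State the condition.** Where the range has a limit on the side of the symbol, the labels differ when a '> *c*' result has an upper limit of *c* + *d* or more, or a '< *c*' result has a lower limit of *c* − *d* or less. The reporting limit must therefore fall short of the matching reference limit. In the six other rows the rules agree, provided the exception is read as covering a parameter with no limit on that side.

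**Step 4. Ask whether 10.4 is really contradicted.** Section 10.4 classifies a value against a range. A bare '> 6' with a range of 4 to 8 cannot be classified that way at all. The Normal in the first row arises only if 6.01 is treated as the measured value, and 13.2 introduces 6.01 for summaries. For such results 13.2 is better read as a blunt convention where the general rule gives no answer.

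**Step 5. Ask which output would change.** The listing flag is assigned to 10.4. The summaries in 13.2 are of results and change, and under SAP section 10 continuous variables are described by n, mean, standard deviation, minimum, median and maximum. These take 6.01 whether the label reads High, Normal or nothing. The SAP text shown names no shift table and no low/normal/high count. Appendix-01 might, but its content is not available.

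**Step 6. Size.** The opening of the SAP says that the study was terminated, that four subjects were randomized and that no formal efficacy analysis will be done. Section 13 restricts the safety analysis to the safety population, so at most four subjects enter any laboratory summary, against about 120 planned.

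**The case for a change.** The best case for a change is that a rule fixed in advance should be sound for whatever the laboratory reports, and this one is not. Its exception has no criterion and can itself mislead. A '< 0.5' result for a parameter with only an upper limit of 0.3 (assumed) would fall to Normal by the exception, although the true value could be above 0.3. The classification sentence does not repeat the summary limitation that opens its paragraph, so a programmer could carry the label into a listing. Tying the label to the reference limit would be a small edit, and the SAP allows revision before the final analysis.

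Much of this stands. The wording is loose, and an unsupported label is logically possible. The step from there to a needed change does not follow. A sentence inherits the scope of its paragraph, and 10.4 already names the rule for listing flags, so an analyst has a workable reading without new text. The obvious repairs also disagree on the one disputed case: comparing 6.01 with a range of 4 to 8 gives Normal, while labelling only when the class is certain leaves the result unflagged. That is a choice between conventions for censored values. The difference from Protocol 11.9.4 adds nothing separate, because the SAP takes precedence.

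**Conclusion.** No change follows, because there is nothing to gain. SAP 13.2 is loosely drafted: it omits the reference range, leaves its exception undefined and does not say which output carries the label. Those gaps can be filled sensibly from the text as it stands, with 10.4 governing the listing flags and the substituted value serving the descriptive statistics.

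The possible effect is a Low or High label on an inequality result whose reporting limit lies inside the reference range, in at most four subjects, in a terminated trial whose output is descriptive. The numeric summaries would be the same either way, and a reader of the listings can compare any result with the printed range. No conclusion about safety is shown to depend on it.

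This rests on three assumptions: that the paragraph's summary scope covers its last sentence, that the unseen table specifications contain no low/normal/high count driven by the symbol rule, and that few or no results were reported as inequalities inside a normal range. The documents can neither confirm nor refute the last two. If the second failed, four individual listings would still let a reader check each label against its range.
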